## 1.0 Objectives / Specific Aims

- Aim 1. Assess the incidence of leukopenia in those randomized to maribavir vs. valganciclovir prophylaxis in adult kidney transplant recipients at high-risk of CMV infection.
  - Hypothesis 1. The incidence of clinically meaningful leukopenia, defined as a WBC count of  $< 3,000$  cells/mm^3 and a reduction in total mycophenolate dose below 1,500 mg/day or valganciclovir dose below 900mg per day (adjusted for renal function), will be significantly lower in the maribavir arm, as compared to the valganciclovir arm.
- Aim 2. Assess the efficacy of maribavir vs. valganciclovir prophylaxis in adult kidney transplant recipients at high-risk of CMV infection.
  - Hypothesis 2. The incidence of CMV infection and disease will be similar between the maribavir arm, as compared to the valganciclovir arm, at 3-, 6-, and 12-months post-transplant.
- Aim 3. Assess the impact of maribavir vs. valganciclovir prophylaxis on healthcare utilization and costs in adult kidney transplant recipients at high-risk of CMV infection.
  - Hypothesis 3. Healthcare utilization will be lower in the maribavir arm, as compared to the valganciclovir arm, at 6- and 12-months post-transplant, driven predominantly by reduced number of telephone calls, televisits, and laboratory monitoring encounters.
- Exploratory Aim 4. Assess the impact of maribavir vs. valganciclovir prophylaxis in adult kidney transplant recipients at high-risk of CMV infection on patient-reported outcomes for quality of life and satisfaction.
- Exploratory Aim 5. Assess any differences in leukopenia, efficacy, healthcare utilization and patient reported outcomes by race and sex in patients randomized to maribavir vs. valganciclovir prophylaxis in adult kidney transplant recipients at high-risk of CMV infection.

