### 3. Recipient of investigational, non-FDA approved medication

#### 6.0 Number of Subjects

70 patients will be randomized 1:1 (35 in each arm) in blocks of 10. Once a patient is randomized and receives at least one dose of CMV prophylaxis medication they will be included in the study in an intent-to-treat manner. Those that are lost to follow-up, withdraw, or are taken off study drug will not be replaced.

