If necessary, multivariable analysis assessments for Aims 1 and 2 will be conducted using Cox regression time to event models. The primary variable of interest in these models will be treatment (maribavir vs. valganciclovir). If necessary and appropriate given event rates, Cox regression analysis will also be used for survival analyses involving all time to event outcomes, including time to acute rejection, time to graft loss and time to death. Models will be adjusted for key variables known to influence outcomes, including CMV serostatus and rATG induction. To prevent overfitting, no more than one covariate for every 5 events will be included in these models. Given the small sample size and expected event rates, Cox models will likely be overfit if including >2 covariates plus the primary treatment variable. Thus, multivariable modeling will be limited to only include key baseline variables that are known to influence the risk of CMV infection and that significantly differ by treatment arm based on preliminary univariate analyses; this will most likely only include CMV D+/R- serostatus and/or rATG induction. Prior to conducting Cox regression, modeling assumptions will be assessed, including proportionality of hazards across treatment arms and assessing the optimal functional forms of non-dichotomous covariates.

For Aim 3, total hospital charges and healthcare utilization will be modeled using a validated method we have used in previous studies. This will be a two-part statistical models for zero-heavy continuous data. The general format of the suggested model in which we fit a logistic model for the probability of non-zero response and a conditional generalized linear model (GLM) for the mean response given that it is non-zero. We will consider several distributions for the GLM part (eg, log-normal, gamma and Weibull, zero-inflated negative binomial [ZINB]) and the best fitting model will be selected using Bayesian information criterion (BIC). Parameter estimates of percent change in total hospital charge per unit increase in the values of each covariate in the model and their 95% CI will be computed using SAS Proc FMM.

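### The only Aim 3 effect named with a confidence interval applies to patients with some use, and no step turns it into a per-patient comparison of the arms

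*Combined protocol and SAP*

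**What the plan says.** Section 1.0 sets the question at arm level: "Assess the impact of maribavir vs. valganciclovir prophylaxis on healthcare utilization and costs in adult kidney transplant recipients". Hypothesis 3 reads "Healthcare utilization will be lower in the maribavir arm, as compared to the valganciclovir arm, at 6- and 12-months post-transplant", and goes on to attribute the fall mainly to fewer phone calls, televisits and laboratory visits. It names utilization only; cost enters through the Aim 3 wording and item 16 of section 4.0. Section 6.0 says of patients who are randomised and take at least one dose that "they will be included in the study in an intent-to-treat manner".

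For Aim 3, Statistical Methods plans "two-part statistical models for zero-heavy continuous data". In the first part "we fit a logistic model for the probability of non-zero response"; the second is "a conditional generalized linear model (GLM) for the mean response given that it is non-zero". The distribution of the second part is to be chosen by BIC. The effect to be reported with a 95% CI is described as "Parameter estimates of percent change in total hospital charge per unit increase in the values of each covariate in the model". The section describes no combination of the two parts, no joint test, and no rule for which part answers Aim 3.

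**The concern.** A two-part fit gives two treatment effects: one on the chance of any use, and one on the mean among patients with some use. Only the second can be expressed as a percent change in charges, so the named estimate compares users on maribavir with users on valganciclovir. Use occurs after randomisation, and treatment is expected to affect it, so the two groups of users need not be comparable. A good distributional fit does not change this.

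If maribavir mainly removes short, cheap encounters, the remaining users are the costlier ones. The reported percent change can then rise while cost per patient falls. The logistic part would point the other way, and the plan does not say how to draw a conclusion from the pair.

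**Working it through.** **Inputs.** From the documents: 35 per arm and intent-to-treat inclusion (section 6.0), and the two-part model with its named effect (Statistical Methods). The plan gives no effect size, power or sample size for Aim 3, so there is no figure to reproduce. It also gives no share of zeros and no costs; every user share, mean and distribution below is an assumption.

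**Step 1: where the percent change comes from.** A logistic coefficient gives an odds ratio. A percent change in charges therefore comes from the non-zero part and equals μT/μC − 1, where μ is the mean among users (T maribavir, C valganciclovir). If the log-normal is chosen, the coefficient is a ratio of geometric means. If the zero-inflated negative binomial is chosen, its count part refers to a latent class rather than to observed users. None of these is an arm-mean ratio.

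**Step 2: the identity.** With p the share of users, mean per patient = p × μ, so

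arm-mean ratio = (pT/pC) × (μT/μC).

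The named effect omits the first factor.

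| pC | pT | μT/μC | Named change | Change in arm mean |
|---|---|---|---|---|
| 50% | 35% | 1.00 | 0% | 0.35/0.50 − 1 = −30% |
| 50% | 30% | 1.25 | +25% | 0.30 × 1.25/0.50 − 1 = −25% |
| 50% | 40% | 1.25 | +25% | 0.40 × 1.25/0.50 − 1 = 0% |
| 95% | 90% | 1.00 | 0% | 0.90/0.95 − 1 = −5.3% |
| 100% | 100% | 0.75 | −25% | −25% |

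The gap closes as the user share approaches 100% in both arms.

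**Step 3: simulation with gamma costs** (35 per arm, shape 1.5, 4,000 trials, two-sided 5%). The combined test uses log(pT/pC) + log(μT/μC) with a delta-method standard error.

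| pC, pT, μT/μC | Average users-only estimate | Average combined estimate | Users-only estimate above 0 | Significant: users-only / combined / logistic |
|---|---|---|---|---|
| 50%, 35%, 1.00 | −1% | −31% | 49% | 6% / 15% / 21% |
| 50%, 30%, 1.25 | +23% | −28% | 74% | 12% / 11% / 39% |
| 50%, 40%, 1.25 | +24% | −1% | 77% | 12% / 6% / 11% |
| 60%, 30%, 1.00 | −1% | −52% | 50% | 6% / 37% / 70% |
| 100%, 100%, 0.75 | −25% | −25% | 7% | 31% / 32% / none (no zeros) |

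**Step 4: equal arm means with log-normal costs** (35 per arm, 6,000 trials). User means are set so that 0.60 × 20 = 0.40 × 30 = 0.30 × 40 = 12 units per patient. The users-only test is a t-test on log cost; the all-patient test is Welch's, zeros included.

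- Users 60% versus 40%: the users-only test rejects 20% of the time (log SD 1.0) or 31% (log SD 0.8).
- Users 60% versus 30%: 42% or 58%.
- The all-patient test rejects 5% to 6%.

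Repeat runs agree to within about 3 points. Nearly all users-only rejections say maribavir costs more. They are correct about users, whose means do differ by construction; they mislead only when read as the answer to Aim 3.

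**Step 5: a saving that raises the users-only ratio.** Suppose 30% of patients in each arm have a 30-unit admission, and an 8-unit admission occurs in 35% on valganciclovir and 5% on maribavir. Mean per patient is 0.30 × 30 + 0.35 × 8 = 11.8 versus 0.30 × 30 + 0.05 × 8 = 9.4, a fall of about 20%. Mean among users is 11.8/0.65 = 18.2 versus 9.4/0.35 = 26.9, a ratio of 1.48. In simulation with log SD 0.8, the arithmetic ratio exceeds 1 in about 84% of trials. The geometric ratio that a log-normal fit reports has a median of about 1.7 and exceeds 1 in about 93% to 94%.

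**The case against.** The strongest reply is that the plan fits both parts. If users fall from 60% to 30% at the same cost per user, the users-only test has about 5% power and an all-patient mean comparison about 32%. A reader might infer that the plan gives up 27 points of power, or that it would miss a real saving. The documents do not support that: the logistic part is planned, and it detects this scenario about 70% of the time, more often than the all-patient mean. In the step 5 example, users fall from 65% to 35%, which the logistic part also detects about 71% of the time. What remains is that the logistic part gives no cost difference and has no stated role in the conclusion.

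Second, Hypothesis 3 expects fewer calls, televisits and laboratory encounters, which is not the same as fewer patients with any use. The schedule in section 10.0 has blood tests for every patient at weeks 2 and 4 and months 3, 6 and 12, so laboratory use should be near universal and the two estimates nearly coincide. This stands and limits the scope. It does not remove the point, because the plan itself expects many zeros and item 16 of section 4.0 analyses by encounter type, including hospitalizations, ED visits and telemedicine.

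Third, Statistical Methods opens with generic t-tests and Mann-Whitney tests that could include all patients. Nothing excludes them, but they are not assigned to Aim 3, whereas the two-part model is.

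Fourth, Aim 3 is secondary in a trial that section 10.0 itself describes as small and exploratory, and the magnitudes are assumed. Both are true. The larger rejection rates need user means 50% to 100% higher on maribavir, exactly offsetting the fall in users.

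**Conclusion.** The point holds in a limited form. The one Aim 3 effect named with a confidence interval is conditional on non-zero use. No step returns it to a contrast per randomised patient, and nothing settles a disagreement between the two parts. That follows from the plan's wording and the identity, without simulation.

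The size depends on inputs that the documents do not give. Under the assumed equal-mean scenarios the users-only test rejects about 20% to 58% of the time, against 5% to 6% for all patients; in the milder gamma case (50% versus 40% users, user mean +25%) it is 12% against 6%. The point matters for hospitalizations, ED visits, possibly televisits and calls, and for charges if the transplant admission is excluded, which the plan does not state. It largely disappears where nearly every patient is a user.

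Two wider readings should be avoided. The documents state no null of equal cost per randomised patient; the arm-level target is inferred from Aim 3 and intent-to-treat inclusion. Nor do they show that the two-part model as a whole is insensitive to a saving. This is worth correcting before analysis, but it concerns a secondary outcome and leaves the primary analysis untouched.

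**What to change.** Name as the Aim 3 estimate the difference and ratio, maribavir versus valganciclovir, in mean cost or encounters per randomised patient in the intent-to-treat set, zeros included. Obtain it from the same two-part model: predicted probability of use times predicted mean among users, averaged by arm, with a bootstrap 95% CI. State that this estimate decides Aim 3. Report the logistic and non-zero parts as components, and label the non-zero part as applying among patients with any use. State also whether the transplant admission counts in total charges, since that determines whether charges have zeros at all.

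The cost is a sentence or two of analysis wording and a short bootstrap step, with no new data. The downside is a wide interval at 35 per arm: in the gamma scenarios that combine zeros with a true saving, power for the combined estimate was only about 10% to 37%. The change corrects what is estimated; it does not make Aim 3 well powered.

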### **Additional Measures**

14. BK Infection (Exploratory Outcome) – defined as BK viremia of at least 2,000 copies/mL. Severe BK infection will be defined at BK viremia of at least 10,000 copies/mL. BK nephropathy will be defined based on the pathology report from the kidney allograft biopsy. The severity and duration of BK infection will be recorded for all patients.
15. Non-CMV, Non-BK Infections (Exploratory Outcome) – defined as any diagnosed and treated infection that leads to hospitalization, and will be sub-classified as bacterial, viral, or fungal etiologies. Opportunistic infections will also be sub-classified for this study as viral, bacterial, or fungal and defined as infections not seen in immunocompetent individuals. The study coordinator capturing clinical event data will review the medical record to determine the timing, severity, treatment regimen and cure time of each infection episode.
16. Healthcare Utilization (Secondary Outcome) – each encounter will be captured during the 12-month study and classified as hospitalizations, ED visits, ambulatory care visits, ambulatory care procedures, radiology encounters, telemedicine visits, telephone calls, and laboratory encounters. Only MUSC encounters will be captured. Data will be analyzed based on utilization type and provider type (Transplant vs. Other). Healthcare charges will be captured from MUSC hospital accounting. Charges will be converted to estimated costs using the Medicare Cost-to-Charge Ratio (CCR) for MUSC. This endpoint will be assessed at 3-, 6-, and 12-months post-transplant.
17. Health-Related Quality of Life (Exploratory Outcome) – the PROMIS QOL will be used to assess health-related quality of life. This questionnaire will be administered to patients at 3-, 6-, and 12-months post-transplant. Results will be compared between study arms.
18. Patient Satisfaction (Exploratory Outcome) – a validated survey provided by will be used to assess patient experience and satisfaction. This instrument will be administered at 3-, 6-, and 12-months post-transplant.

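### Aim 3 lists zero-inflated negative binomial as a distribution for responses already restricted to be non-zero, and uses one two-part model for both charges and encounter counts

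*Combined protocol and SAP*

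**What the plan says.** The Aim 3 paragraph of Statistical Methods (Section 10.0) covers two kinds of response at once: "total hospital charges and healthcare utilization will be modeled using a validated method we have used in previous studies". The model class is "two-part statistical models for zero-heavy continuous data". In the first part, "we fit a logistic model for the probability of non-zero response"; the second is a "conditional generalized linear model (GLM) for the mean response given that it is non-zero". The candidates for the second part follow: "We will consider several distributions for the GLM part (eg, log-normal, gamma and Weibull, zero-inflated negative binomial [ZINB". The choice among them is then mechanical: "the best fitting model will be selected using Bayesian information criterion (BIC". The only effect measure named is a percent change in total hospital charge with a 95% interval. None is named for utilization.

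Section 4.0, item 16, defines utilization as encounters "classified as hospitalizations, ED visits, ambulatory care visits, ambulatory care procedures, radiology encounters, telemedicine visits, telephone calls, and laboratory encounters", analysed by type and by provider type. Only encounters at the study centre count, and charges come from its hospital accounting.

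The documents do not say:
- whether total hospital charges include outpatient encounters or the index transplant admission;
- what share of zeros is expected;
- which distribution belongs to which response;
- on which patients and on what scale BIC is computed.

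**The concern.** The second part of the model is conditional on a non-zero response and is described as continuous. ZINB is neither: it is a probability mass on 0, 1, 2, ... with an extra component for zeros. Once the logistic part has taken the zeros out, ZINB has none left to describe, yet it still reserves probability for them. For charges it is the wrong kind of distribution. For encounter counts it is the only count model named, and it is named for the wrong subset of patients.

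The zero-heavy premise raises a second problem. Hypothesis 3 in Section 1.0 rests mainly on telephone calls, televisits and laboratory encounters. All are counts, and some are generated by routine follow-up that every patient has. A total that includes such encounters may contain no zeros, and the plan has no one-part fallback.

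At stake is the family behind the reported charge and utilization effects. The analyst would have to depart from the written rule after seeing the data, in an open-label trial.

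**Working it through.** The documents give no figure for Aim 3 (no zero share, mean, SD or BIC), so there is nothing to reproduce. From the documents come n = 70 (Section 6.0), recruitment of recipients transplanted at the centre (Section 5.0), and history and physical plus CBC/BMP at 3, 6 and 12 months (Section 10.0 table). All other inputs below are assumptions for illustration.

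**1. ZINB on positive-only counts.** Assumed: 5,000 simulated patients with negative binomial counts, mean 1.0 and shape 1.2. Zeros were 48.04%, leaving 5,000 × (1 − 0.4804) = 2,598 positive counts.
- The ZINB zero-inflation probability went to its boundary (about 2 × 10⁻¹⁰), so that parameter is not identified.
- The dispersion also degenerated to the Poisson limit, with fitted mean 1.933. The implied P(0) is exp(−1.933) = 0.145, in a subset where zero is impossible.
- A zero-truncated negative binomial recovered mean 0.94 and shape 1.02, close to the truth.
- BIC was 8,278.8 for ZINB and 6,973.1 for the zero-truncated model, a gap of 1,305.7, or about 0.50 per positive count. With 70 patients and the same zero share there would be about 70 × 0.52 = 36 positive counts, so a gap of very roughly 18.

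**2. BIC on charges.** Assumed: 70 log-normal charges, median $60,000, log-SD 0.9. ZINB was fitted to charges rounded to the unit shown.

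| Unit | Log-normal | Gamma | Weibull | ZINB |
|---|---|---|---|---|
| Dollars | 1700.0 | 1704.2 | 1709.5 | 1708.5 |
| Thousands | 732.9 | 737.1 | 742.5 | 741.7 |

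- Among the three continuous families the order is the same in both units. Gamma minus log-normal is 4.2 in both, and Weibull minus log-normal is 9.5 and 9.6 (rounding). Over 500 simulated trials of 70, BIC picked the true log-normal 91% of the time.
- ZINB in dollars is the gamma value plus the penalty for one unused parameter: 1704.2 + ln(70) = 1704.2 + 4.2 = 1708.4, against 1708.5 fitted. It carries no information about zeros.
- Scale does matter in one way. A normal model on log charges without the Jacobian term has BIC 169.4, against 1700.0 for the identical log-normal fit on the original scale.

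**3. Zeros and the logistic part.** With per-patient zero probability p, expected zeros are 70p and P(no zeros) = (1 − p)^70.

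| Assumed p | Expected zeros | P(no zeros) |
|---|---|---|
| 0.01 | 0.7 | 0.49 |
| 0.05 | 3.5 | 0.03 |
| 0.30 | 21 | about 0 |
| 0.50 | 35 | about 0 |

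The first two rows describe a total that includes scheduled visits and laboratory tests or the index admission. The last two describe single types such as readmissions or ED visits. The logistic part is empty or fragile in the former and workable in the latter.

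**The case against.** The fairest defence is that one sentence serves two responses, with an open list introduced by eg, so the intended reading is continuous families for charges and ZINB for encounter counts. That is probably what was meant. It does not rescue the wording, because ZINB still sits in the part conditional on a non-zero response, and no listed family suits positive counts.

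A second defence is that zeros may well exist. Total hospital charges is undefined, the method reference concerns hospitalization costs, and an inpatient reading without the index admission would give zeros for patients never readmitted. Item 16 also analyses utilization by type, counts only encounters at the centre, and sits beside a statement in Section 10.0 that some laboratory work is done elsewhere. This stands. It means that absence of zeros depends on a definition the plan omits. It is also true that with no zeros the logistic part drops out and the GLM can be fitted to everyone, so a missing fallback is a gap and not a failure of the analysis.

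A reader might go further and infer that BIC cannot rank the candidates at all because it changes with the currency unit. The documents do not support that. Log-normal, gamma and Weibull on the same untransformed charges all shift by the same constant, which cancels. Only ZINB, or a log-scale fit without the Jacobian, breaks the comparison. In the same-unit illustration ZINB would not have been selected.

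**Conclusion.** The point holds in a limited form. Listing ZINB for a GLM conditional on a non-zero response is wrong as written: it models zeros twice, does not suit continuous charges, and puts a probability mass beside densities in a BIC ranking. Encounter counts are left without a suitable model. This follows from the wording of the Aim 3 paragraph alone. The simulated sizes (P(0) of 0.14, and the BIC gaps) rest on assumed inputs and only illustrate it.

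The zero-heavy form fits some Aim 3 outcomes and not others. Which ones depends on what total hospital charges include, which is not stated. It would be too strong to conclude that the Aim 3 analysis cannot work: the two-part form is reasonable for outcomes such as hospitalizations and ED visits, and BIC selection among the continuous families is sound.

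The change should be made, but the consequence is bounded. Healthcare utilization is a secondary outcome, Section 10.0 describes the trial as small and exploratory, and the primary leukopenia analysis is untouched.

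**What to change.** Rewrite the Aim 3 paragraph by outcome type:

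- Remove ZINB from the conditional GLM part.
- Model charges with a continuous family (log-normal, gamma or Weibull). BIC selection can stay, computed on the same patients and the same untransformed scale for every candidate. Naming one family in advance, such as gamma with a log link, is an acceptable alternative but a matter of preference.
- Model encounter counts on all patients by negative binomial with log follow-up time as offset, reporting a rate ratio. If zeros are excessive, use ZINB on all patients, or a hurdle model with a zero-truncated count part. The offset is needed because Section 14.0 censors withdrawn patients; at the expected 3–5% dropout that is 35 × 0.03 = 1.05 to 35 × 0.05 = 1.75 patients per arm.
- Use the logistic part only for outcomes with zeros, such as readmission or ED charges, and state that a one-part model applies otherwise.
- Define total hospital charges: outpatient encounters in or out, index admission in or out.

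The cost is SAP wording, a little analysis work and slightly less freedom in choosing the distribution. No data collection changes.

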For Aim 4, survey results will be aggregated using validated methods for each survey. The mean scores will be compared between treatment arms, as well as the mean change across the three measurement timepoints. Comparisons will be made using standard statistical tests based on the distribution of the results (Student's t-test for normal variance or the Mann-Whitney test for non-normally distributed data). Mean change will be assessed using general linear modeling (GLM) for repeated measures data with the appropriate link based on the distribution of the measures.

For Aim 5, interaction terms will be added to multivariable models (Cox regression or GLM) to assess if there are differences by race (race\*treatment) or sex (sex\*treatment). A p-value of <0.1 will be considered sufficient evidence of likely effect modification and the analysis will then be stratified by the appropriate variable (either race or sex) for a given outcome if there is in fact a significant interaction. Given the limited sample size, there is likely low power to detect statistically significant differences for this Aim; thus Aim 5 is considered exploratory in nature.

We will also assess for any impact of maribavir on tacrolimus dosing or trough concentrations. Steady-state stable doses of tacrolimus (mg/day) and whole blood trough concentrations will be assessed and compared in patients during maribavir therapy versus after completion of therapy. Changes will be compared between the treatment arms using difference in difference methodology to assess for drug-drug interactions. The level-normalized dose (dose needed to achieve a level of 8 ng/mL using linear proportions) will also be compared using difference-in-difference analysis. Finally, the proportion of patients in the maribavir arm that have more than a 10% change in level-normalized dose after discontinuing maribavir therapy will be collected and reported. These analyses are considered exploratory.

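### Exploratory Aim 5 takes any race or sex interaction with p<0.1 as sufficient evidence of likely effect modification, with no multiplicity control over at least eight tests; the chance of a false declaration is roughly one in three to seven in ten.

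*Combined protocol and SAP*

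**What the plan says.** Section 1.0 defines Exploratory Aim 5 as: "Assess any differences in leukopenia, efficacy, healthcare utilization and patient reported outcomes by race and sex". That is four outcome domains and two modifiers.

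Under Statistical Methods in Section 10.0, "interaction terms will be added to multivariable models (Cox regression or GLM) to assess if there are differences by race", and likewise by sex. The trigger reads: "A p-value of <0.1 will be considered sufficient evidence of likely effect modification and the analysis will then be stratified by the appropriate variable". It is applied outcome by outcome, for race or for sex. The same paragraph says that power is probably low and that Aim 5 is therefore exploratory.

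The plan does not limit the number of interaction tests or adjust for them. It does not name one outcome and time point per domain, or say whether the interaction p-value comes from a Wald, score or likelihood-ratio test.

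For the Cox models the plan also sets a limit: "no more than one covariate for every 5 events will be included in these models".

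**The concern.** A 0.1 threshold is a common screen for a single interaction. Here it applies separately to every outcome and modifier, and one hit is enough for the plan to speak of sufficient evidence and to stratify that outcome. Over eight or more tests, a chance hit somewhere is a realistic prospect. The plan's caveat about low power warns that real differences may be missed. It does not warn that a difference found may be false.

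The primary outcome adds a second difficulty. Few leukopenia events are expected on maribavir, and splitting them by race or sex will often leave one subgroup with none. Common interaction tests behave very differently in that situation.

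At stake is what the trial may say about race and sex. Outcomes picked out by this rule would tend to show exaggerated subgroup differences, under wording that presents them as established.

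**Working it through.** The documents give no error rate for Aim 5, so there is no stated figure to reproduce on that point. The plan's covariate limit can be checked. At 35% versus 5% with 35 per arm (Power/Sample Size), expected leukopenia events are 35 × 0.35 + 35 × 0.05 = 12.25 + 1.75 = 14. Then 14 / 5 = 2.8, so two covariates, which agrees with the plan's own remark about overfitting.

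**1. Number of tests.** Four domains × two modifiers = 8, as a floor. Section 1.0 names two outcomes under efficacy ("The incidence of CMV infection and disease will be similar between the maribavir arm") and two under patient-reported outcomes ("on patient-reported outcomes for quality of life and satisfaction"). Counted separately, that makes six outcomes × two modifiers = 12 tests.

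**2. Independent tests at exact size 0.10, no effect modification anywhere.** P(at least one hit) = 1 − 0.9^k.
- k = 8: 1 − 0.9^8 = 0.570, with 8 × 0.1 = 0.8 false hits expected.
- k = 12: 1 − 0.9^12 = 0.718.

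**3. Correlated tests.** The documents give no correlations, so a range is assumed. The simulation uses two-sided normal test statistics, equally correlated within each modifier, with race tests independent of sex tests.

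| Correlation | 8 tests | 12 tests |
|---|---|---|
| 0 | 57% | 72% |
| 0.2 | 56% | 70% |
| 0.4 | 52% | 64% |
| 0.5 | 49% | 60% |
| 0.7 | 42% | 50% |
| 0.9 | 32% | 36% |

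**4. Tests below nominal size.** With so few events, a simulated Wald interaction test for leukopenia rejects in about 0.4% of null trials on a log-hazard scale and 0.7% on a logit scale. At an assumed 16% event rate in both arms, taken here to stand for an efficacy outcome, it rejects in about 4.6%. Treating tests as independent:
- Eight tests, Wald undersized for leukopenia only: 1 − 0.996² × 0.9^6 = 0.473.
- Eight tests, undersized for leukopenia and efficacy: 1 − 0.993² × 0.954² × 0.9^4 = 0.411.
- Twelve tests, undersized for leukopenia, infection and disease: 1 − 0.993² × 0.954^4 × 0.9^6 = 0.566.

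**5. Empty cells for leukopenia.** Assume two equal subgroups, so 17 and 18 maribavir patients per subgroup at a 5% rate. P(at least one has no event) = 1 − (1 − 0.95^17)(1 − 0.95^18) = 1 − 0.582 × 0.603 = 0.65. Empty valganciclovir cells add almost nothing (0.65^17 is below 0.001).

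**6. What the choice of test does.** With an empty cell the interaction estimate runs to infinity with a very large standard error, so a Wald test does not reject. A likelihood-ratio test remains usable and rejects in about 10% to 11% of null trials, close to nominal. As one deliberately extreme illustration, suppose one subgroup has 35% in both arms and the other 35% versus 2%. The Wald test then detects the difference in about 12% to 14% of trials, the likelihood-ratio test in about 80%.

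**The case against.** The strongest reply is that Aim 5 is labelled exploratory in Section 1.0 and again in Statistical Methods, that Section 10.0 calls the whole trial small and exploratory, and that the rule speaks only of *likely* effect modification. The direct consequence of p<0.1 is a stratified analysis, and no confirmatory claim rests on it. That stands, and it limits the seriousness of the point. It does not answer it: the reason given for the exploratory label is low power, and the preceding sentence tells the reader that a hit is sufficient evidence.

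Some stronger readings are tempting but not supported.
- *A false declaration is more likely than not.* This is true only under conditions. With eight tests it fails once within-modifier correlation reaches about 0.5, or if sparse-event Wald tests are used.
- *The risk is higher still because outcomes are assessed at 3, 6 and 12 months.* A Cox model uses follow-up in one fit, and change in the survey scores is a single repeated-measures analysis. Nothing says that each interaction is tested three times.
- *The interaction models break the covariate limit.* The plan counts treatment separately, so the modifier and its interaction fit within two. An excess arises only if an adjustment covariate is also kept, and adjustment is conditional.
- *Subgroup results for other outcomes would be withheld.* The plan says when an analysis is stratified, not that other interaction results go unreported.
- *The rule cannot detect real modification of leukopenia.* That needs a Wald test, which the plan does not name; a likelihood-ratio test does not share the fault.

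**Conclusion.** The point holds in conditional form. With no effect modification anywhere, the Aim 5 rule has roughly a one-in-three to seven-in-ten chance of at least one false declaration. The main case is about 57% (eight independent tests at nominal size). The low end, 32%, is eight tests with within-modifier correlation 0.9; the high end, 72%, is twelve independent tests. Even the low end is a weak basis for calling a single hit sufficient evidence.

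For leukopenia, the conclusion could turn on a software default. About 65% of trials would have an empty cell, where a Wald test does not reject and a likelihood-ratio test keeps roughly nominal size.

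These figures assume two-sided tests, the plan's 35% and 5% rates, two equal subgroups (the documents give no race or sex mix), and simple approximations to the Cox model. Because the aim is exploratory, this is a worthwhile and cheap improvement, not a threat to the primary analysis.

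**What to change.** In the Aim 5 paragraph of Statistical Methods:
- Name one outcome and one time point per domain, for example leukopenia yes/no, CMV infection yes/no, total encounters and PROMIS score, each at 12 months.
- For all of these, report the treatment effect with 95% CI in each race and sex group, and the interaction estimate with its CI, whatever the p-value.
- Replace the sufficient-evidence wording with a statement that the findings are hypothesis-generating, and give the number of comparisons (eight, if one outcome per domain is named).
- For the sparse binary outcomes, specify a likelihood-ratio, exact or score method in place of a Wald test. Moving from the planned models to risk differences is optional.

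The cost is a wording change and a few extra descriptive tables, with no new data or patients. The sponsor gives up declaring effect modification from a single p<0.1.
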